5.3.5.9 Lack of Efficacy or Worsening of Unclassifiable ILD

Events that are clearly consistent with the expected pattern of progression of the underlying disease should not be recorded as adverse events. These data will be captured as efficacy assessment data only. In most cases, the expected pattern of progression will be based on $\geq 10\%$ relative decline in FVC or a >50 m decline in 6MWD. In rare cases, the determination of clinical progression will be based on symptomatic deterioration or a decline in DLco of $\geq 15\%$. However, every effort should be made to document progression through use of objective criteria. If there is any uncertainty as to whether an event is due to disease progression, it should be reported as an adverse event.

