4.2.1 Study Days

Study days will be defined as the number of days since randomization, and is calculated as:

- Study day = Assessment date randomization date + 1, for assessments on or after the randomization date.
- Study day = Assessment date randomization date, for assessments before the randomization date.

The day of randomization will be study day 1.

Pirfenidone — F. Hoffmann-La Roche Ltd

4.2.2 Baseline and Screening Observations

Table 1 Definition of Baseline and Screening Observations

| | Definition |
|----------------|---|
| Baseline data | Baseline is defined as the last valid assessment prior to first intake of randomized study drug (pirfenidone/placebo). |
| | This may not be the same as the Day 1 (Week 1) visit as per eCRF. In case that Day 1 (Week 1) visit data is missing and the randomized treatment is given, data from the screening period will be used as baseline. In addition, if randomized treatment is not given then baseline will be defined as the last valid assessment collected either screening or day 1. |
| | Generally, it is assumed that measurements referring to the Day 1 (Week 1) visit have been performed before randomized study drug (pirfenidone/placebo) was given. |
| | Adverse events occurring on the date of first randomized pirfenidone/placebo treatment will not be considered baseline, but treatment-emergent. |
| Screening data | Screening measurements are all the measurements performed before the randomization date. |

4.2.3 On-treatment Assessments for Efficacy Analyses (Double-blind Treatment Period)

For efficacy analyses, on-treatment assessments will be the assessments performed on or after the randomization date until the double-blind treatment completion or discontinuation date.

4.2.4 On-treatment Assessments for Safety Analyses (Double-blind Treatment Period)

For safety analyses, on-treatment assessments will be the assessments performed on or after the first dose of randomized pirfenidone/placebo date until the last positive dose of randomized treatment plus 28 days.

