Pirfenidone — F. Hoffmann-La Roche Ltd

The values of the parameters recorded for the 6MWD test are:

- Vital signs (Heart rate (beats/min), systolic blood pressure (mmHg), diastolic pressure (mmHg)) (before the test, at the end of the test)
- Distance walked (m),
- Oxyhemoglobin saturation (SPO2) (before the test (at rest), at the end of the test),
- Oxygen (O2) requirements (L) for patients who received oxygen (at the end of the test)

will be summarized descriptively by treatment arm.

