- Progression free survival (PFS), defined as the time to the first occurrence of a >10% absolute decline in percent predicted FVC, a >50 m decline of 6MWD, or death from any cause, will be analyzed using Kaplan-Meier techniques:
 - KM plots of time to first occurrence of the combined primary efficacy endpoint will be provided by treatment arm.
 - Frequencies and percentages of patients with events and patients censored will be provided. Descriptive statistics of KM estimates of PFS (weeks) will be presented.
 - The PFS of two randomized treatment arms will be compared with a logrank test.
 - Hazard ratios and corresponding 95% CI will be calculated by applying Cox-proportional hazard models.
- An alternative definition of PFS (also in weeks), namely the time to the first occurrence of a >10% relative decline in FVC, non-elective respiratory hospitalization, or death, will be analyzed using Kaplan-Meier techniques as Pirfenidone — F. Hoffmann-La Roche Ltd

- defined for the point above; and the two treatment arms will be compared with a log-rank test. In addition, hazard ratios and corresponding 95% CI will be calculated by applying Cox-proportional hazard models
- Time to death from any cause and time to death from respiratory diseases
 assessed by the SOC "Respiratory, thoracic and mediastinal disorders" (in weeks)
 will be analyzed using Kaplan-Meier techniques as defined above; and the two
 treatment arms will be compared with a log-rank test. In addition, hazard ratios
 and corresponding 95% CI will be calculated by applying Cox-proportional
 hazard models.

For all secondary endpoints p-values will be reported in a descriptive fashion. No multiplicity adjustments for statistical testing will be done.

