4.5.4 Exploratory Efficacy Endpoints

The exploratory objectives for this trial are to evaluate the role of MMF treatment in ILD and to investigate potential biomarkers associated with fibrosis and ILD.

For the MMF objective, primary and selected secondary endpoints will be investigated by means of a subgroup analyses that stratifies patients according to whether they received MMF treatment. In addition, the overall safety summary will be presented by this subgroup. The selected secondary endpoints are:

- Deaths from any cause and respiratory disease-related
- Hospitalizations from any cause and respiratory disease-related

The analysis of these exploratory efficacy endpoints by subgroup are defined under section Section 4.5.6.

The mean FVC decline in each treatment arm will be calculated as in the primary analysis for the subgroups of patients that received MMF treatment and compared using a student's t-test.

Other exploratory efficacy endpoints are discussed in the sensitivity and subgroup sections (see Section 4.5.6 and Section 4.5.7, respectively).

Moreover, additional categorical analyses for the percent predicted DLco and 6MWD will be presented as exploratory:

- Categorical change of >15% absolute decline from baseline to week 24 in percent predicted DLco will be compared between the treatment arms using a logistic regression.
- Categorical change of >50% absolute decline from baseline to week 24 in 6MWD
 (m) will be compared between the treatment arms using a logistic regression.

Pirfenidone — F. Hoffmann-La Roche Ltd

For the biomarker objective, assessments of the exploratory biomarkers and their relationship with drug responses will be described in a separate analysis plan.

A correlation analysis of individual patient slopes estimated by linear regression models between those obtained for home spirometry and site spirometry were performed to assess the concordance of the data obtained by the two methods.

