4.5.7 Subgroup Analyses

Subgroup analyses will be conducted for the exploratory endpoint, as described in Section 4.5.4. The following subgroups will be based on:

- The four groups resulting from combinations of the two stratification factors:
 - Concomitant MMF treatment (yes/no)
 - o Presence/absence of IPAF as defined by the MDT
- Gender: Male, Female
- Age (years): <65 years, ≥ 65 years
- Percent predicted FVC at Baseline: <65%, ≥65% to < 80%, ≥80%
- Percent predicted DLco at Baseline: <35%, ≥35%
- Body weight: <60 kg, ≥60 kg
- Previous Biopsy (yes/no)

4.5.8 Sensitivity Analyses for missing data

The robustness of the primary method of estimation described above will be explored by a series of sensitivity estimators based on varying assumptions underlying the multiple imputation strategy.

As the primary analysis for this study was performed in March 2019 the number of patients with missing FVC values at week 24 are known. No data was collected after treatment discontinuation.

3 different approaches will be used to evaluate the robustness of the analysis of the secondary endpoint to the missing at random (MAR) assumption.

Due to the low number, deaths and other intercurrent events have not been considered in the multiple imputation analysis.

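### SAP 4.5.4 prints the exploratory 6MWD decline cut-off as a percentage labelled absolute on a scale in metres; >50 m is the best-supported reading, and the intended and programmed rule should be confirmed

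*SAP*

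**What the plan says.** SAP version 3.0, Section 4.5.4, adds two exploratory categorical analyses at Week 24, each compared between arms by logistic regression. The first is "Categorical change of >15% absolute decline from baseline to week 24 in percent predicted DLco". The second is "Categorical change of >50% absolute decline from baseline to week 24 in 6MWD", with the variable given in metres. The second definition reads the same in SAP version 2.0, Section 4.5.3.

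Elsewhere 6MWD is a distance in metres: SAP 4.4.3 records it that way, and SAP 2.2.2 lists the secondary endpoint as a change in metres. The PFS definition in SAP 4.5.3 uses "a >50 m decline of 6MWD, or death from any cause". Protocol 5.3.5.9, on the expected pattern of progression, uses "relative decline in FVC or a >50 m decline in 6MWD".

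**The concern.** An absolute change in a variable measured in metres is itself in metres. The DLco definition is coherent because percent predicted DLco is already on a percentage scale. No such scale exists here for 6MWD, so the printed cut-off contradicts itself without reference to any other section.

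Two repairs are possible. Either the percent sign should be metres, or the word absolute should be relative. They define different events. A reader of a table of 6MWD decliners cannot tell which was counted, and a programmer working from the text alone would have to choose. If the choice was the 50% relative fall, the logistic regression could rest on few events.

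SAP version 3.0 itself states, in Section 4.5.8: "As the primary analysis for this study was performed in March 2019". Any correction made now therefore follows the primary results and should be disclosed as such.

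**Working it through.** **Step 1: compare every 6MWD decline cut-off.** The cut-off is a definition, so there is no stated figure to reproduce. The places are:

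| Place | Cut-off |
|---|---|
| Protocol Section 2 (Table 1), 3.1 and 6.4.2, PFS | >50 m |
| Protocol 5.3.5.9, pattern of progression | >50 m |
| SAP v3.0, 2.2.2 and 4.5.3, PFS | >50 m |
| SAP v2.0, 2.2.2 and 4.5.2, PFS | >50 m |
| SAP v3.0, 4.5.4 and SAP v2.0, 4.5.3, exploratory | >50%, labelled absolute |

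No other place uses a 50% criterion for 6MWD.

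**Step 2: convert between the readings.** For baseline B in metres, a 50% relative fall is 0.5 × B. Its strictness relative to 50 m is 0.5 × B / 50 = B / 100.

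| Baseline | 50% fall | Ratio to 50 m |
|---|---|---|
| 100 m | 0.5 × 100 = 50 m | 1.0 |
| 150 m | 0.5 × 150 = 75 m | 1.5 |
| 300 m | 0.5 × 300 = 150 m | 3.0 |
| 400 m | 0.5 × 400 = 200 m | 4.0 |

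The 50% rule is stricter at any baseline above 100 m. Protocol 4.1.1 requires at least 150 m for entry. However, the schedule repeats 6MWD on Day 1, and SAP 4.2.2 takes the last valid pre-dose value as baseline, so an analysis baseline below 150 m is possible.

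**Step 3: an illustration on assumed values.** The documents give no distribution for 6MWD or its change. Assume the change is normal with mean m between −10 and −40 m and SD s between 60 and 100 m, the same in both arms, with one fixed baseline. The share of decliners is Φ((−50 − m)/s) under >50 m and Φ((−0.5B − m)/s) under the 50% rule. Over the values run (m = −10, −25, −40; s = 60, 80, 100):

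| Baseline | >50 m | >50% relative |
|---|---|---|
| 150 m | 25–46% | 14–36% |
| 300 m | 25–46% | 1.0–14% |
| 400 m | 25–46% | 0.08–5.5% |

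For m = −25 and s = 80, the >50 m rule gives (−50 + 25)/80 = −0.3125, or 37.7%. The 50% rule at 400 m gives (−200 + 25)/80 = −2.1875, or 1.4%. With the planned 125 per arm all assessed, that is 0.377 × 125 ≈ 47 decliners per arm against 0.0144 × 125 ≈ 2. At a baseline of 300 m the 50% rule gives 5.9%, or about 7; at 150 m it gives 26.6%, or about 33. The size of the difference depends on baselines that the documents do not report.

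**The case against.** The strongest counter-argument is that the stray word may be *absolute* and not the percent sign. It is tempting to say that this SAP always writes *relative* for a proportional fall, as in "a >10% relative decline in FVC" for the alternative PFS. It does not. SAP 4.5.3 applies >5% and >10% cut-offs to FVC in mL without that word, and SAP 2.2.2 shows that the mL version is a relative change. SAP 4.5.1 excludes home values more than 50% away from baseline site spirometry, again without the word. *Absolute* is also used loosely: SAP 4.5.3 announces an absolute change in 6MWD and then takes the Week 24 distance as the outcome.

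A reader might also cite Protocol 5.3.5.9 as pairing 50 m in 6MWD with 15% in DLco, the same two numbers as in SAP 4.5.4. That section pairs >50 m with the FVC decline. It gives DLco only for rare cases, as at least 15%, and it governs what is recorded as an adverse event. It supports >50 m as the cut-off in use for 6MWD, but not a theory of how the slip arose.

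Finally, an exploratory cut-off need not match the PFS component, so a difference from PFS is not in itself an error.

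All of this stands, and it lowers the certainty of the >50 m reading. None of it removes the contradiction within the definition.

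**Conclusion.** The definition is wrong as written: it states an absolute change in metres as a percentage. Confidence in that is high. That >50 m was meant is the best-supported reading, because all other 6MWD decline cut-offs agree on it, but it is not proven.

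A reader might infer that a wrong analysis was run for the March 2019 results. The documents do not support this. They do not say which rule was programmed or that this exploratory table was produced at that date, and neither the program nor the table shell is included.

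If >50 m was programmed, no result changes. If the 50% rule was run, the event is rarer for any baseline above 100 m. Sparse data are then possible, but how sparse cannot be stated from the documents; the shares and counts of decliners above rest on assumed values.

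The impact is low either way. The analysis is exploratory and does not appear in the protocol's endpoint table or its exploratory section. The primary endpoint, sample size, 6MWD rank ANCOVA and both PFS definitions do not depend on it.

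**What to change.** Check the intended rule and the programmed rule first, against the table shell and the program. Then:

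- If both are >50 m, replace the percent sign in SAP 4.5.4 so that the cut-off is an absolute fall of more than 50 m between baseline and Week 24, and note that no result changes.
- If a 50% relative fall was intended and run, replace *absolute* with *relative* and keep that result. Show the >50 m result beside it, labelled post hoc, with the number of decliners per arm for both rules.
- If intention and program differ, say so, keep the result already produced, and show both rules in the same way.

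The cost is one line of SAP text and a look at an existing program. If the 50% rule was run, or if the two differ, add one exploratory table and a post hoc note.

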4.5.5 Analyses of Patient-Reported Outcomes

Several PRO assessments will be conducted in this trial, including the UCSD-SOBQ, the Leicester Cough Questionnaire, the cough visual analog scale, and the SGRQ.

PRO data will be collected via questionnaires to document the treatment effect and to evaluate the benefit of pirfenidone. The questionnaires, translated into the local language as required, will be completed in their entirety at specified time points during the trial. To ensure instrument validity and that data standards meet health authority requirements, questionnaires will be self-administered before the patient receives any information on disease status and prior to the performance of non-PRO assessments, unless otherwise specified.

St. George's Respiratory Questionnaire (SGRQ)

The St. George's Respiratory Questionnaire (SGRQ) is an index designed to measure and quantifies health-related health status in patients with chronic airflow limitations. The SGRQ is a 50-item questionnaire, addressing the frequency of respiratory symptoms (items 1-8), the patient's current state (sections 9-16). From the 50 items a total score, as well as three component scores (Symptoms, Activities, Impacts) will be derived. The total score ranges from 0, presenting the best possible health status to 100, presenting the worst possible health status.

The change in SGRQ total score will be of primary interest when assessing health-related quality of life (HRQoL).

The analysis of PROs assessed by SGRQ total score and by SGRQ component scores for symptoms, activity, and impacts will be analyzed as follows:

- The absolute score values and changes from baseline for the total and each subscore will be presented descriptively over time by treatment arm.
- Changes from baseline to week 24 or early discontinuation visit will be compared between the treatment arms using a rank ANCOVA with change from baseline as outcome variable and standardized rank baseline value as covariate. This analysis will be done only for the total score.

The SGRQ and the details for calculating the score can be found in Appendix 3.

Pirfenidone — F. Hoffmann-La Roche Ltd

The University of California, San Diego-Shortness of Breath Questionnaire (UCSD-SOBQ)

The University of California, San Diego-Shortness of Breath Questionnaire (UCSD-SOBQ) is a symptom-specific, 24-item, patient-self-administered questionnaire that assesses shortness of breath while doing a variety of activities of daily living. Each of the 24 activities are rated on how dyspnea affects the activity on a 6-point scale: 0 = None at all to 5 = Maximal or unable to do because of breathlessness. The scores will be summarized to a total score, ranging from 0 - 120.

The total score of the UCSD SOBQ will be summarized as follows:

- The absolute total scores and changes from baseline will be presented descriptively over time by treatment arm.
- Changes from baseline to week 24 or early discontinuation visit will be compared between the treatment arms using a rank ANCOVA with change from baseline as outcome variable and standardized rank baseline value as covariate.

Additional details on the UCSD SOBQ can be found in Appendix 3

The Leicester Cough Questionnaire

The Leicester Cough Questionnaire is a patient-reported questionnaire evaluating the impact of cough on quality of life. The questionnaire comprises 19 items and takes 5 to 10 minutes to complete. Each item assesses symptoms, or the impact of symptoms, over the last 2 weeks on a seven-point Likert scale. Scores in three domains (physical, psychological and social) are calculated as a mean for each domain (range 1 to 7). A total score (range 3 to 21) is also calculated by adding the domain scores together. Higher scores indicate better quality of life.

The total score and the physical, psychological and social domain scores of the Leicester Cough Questionnaire will be analyzed as follows:

- The scores and changes from baseline will be presented descriptively over time by treatment arm.
- Changes from baseline to week 24 or early discontinuation visit will be compared between the treatment arms using a rank ANCOVA with change from baseline as outcome variable and standardized rank baseline value as covariate. This analysis will be done only for the total score.

Details on calculating the domain scores can be found in Appendix 3

The Cough VAS

This visual analogue scale is designed to help us learn about the severity of your cough. This scale is 100mm (10cm) in length.

Pirfenidone — F. Hoffmann-La Roche Ltd

The cough VAS score will be summarized descriptively by visit and treatment arm. The change in cough VAS will be analyzed using a rank ANCOVA model. The change in VAS score for cough recorded at 24 weeks will be used as the outcome variable and the standardized rank baseline result will be used as a covariate. Please refer to Appendix 3 for further details.

4.5.6 Sensitivity Analyses

As a sensitivity analysis to the primary analysis, the time-adjusted mean FVC decline will be estimated a random slope and intercept linear regression model, with an absolute change in FVC (mL) as the outcome variable assuming linear decline in lung function over time. The model includes random coefficients for slope and intercept and fixed effect terms for treatment, and covariates to be selected as described below. The statistical model is defined as follows:

$$Y_{ijk} = (\alpha + a_i) + (\gamma + \beta_s T_k + g_i) t_{ij} + \beta_g Cov 1_i + \beta_a Cov 2_i + \epsilon_{ij}$$

- o Y_{ijk} is the value measured for ith patient at time j in treatment group k
- o t_{ij} is the time of measurements for ith patient at study day j
- \circ T_k =0 if patient in Placebo group and T_k=1 is patient in Pirfenidone
- \circ β_s is the effect of Pirfenidone on the slope
- \circ α and γ are elements of the intercept and slope respectively a_i and g_i are random specific components of the intercept and slope for the ith patient
- \circ β_g , β_a are patient specific demographics' coefficients (strata)
- o Cov1_i, Cov2_i are covariates to be included for the ith patient
- ο ε_{ii} is the random error for ith patient at time j
- o a_i and g_i are assumed to be normally distributed with mean 0 and arbitrary covariance matrix
- \circ ε_{ij} are assumed to be independent and normally distributed with mean 0 and variance σ ε²
- Within patient errors follow a random coefficient regression model with random effect for intercept and slope
- An unstructured variance-covariance structure will be used to model the within patient measurements
- The variance-covariance matrix, modeled to estimate the inter-individual variability is considered to have a Variance-Components structure

The model will be applied by adding the stratification factors MMF treatment and IPAF as covariates to the home spirometry data, once taking into account the old and once the new quality flag.

The same model with and without adding the stratification factors as covariates will be applied to the key secondary endpoint of site-measured FVC (mL).

Pirfenidone — F. Hoffmann-La Roche Ltd

4.5.7 Subgroup Analyses

Subgroup analyses will be conducted for the exploratory endpoint, as described in Section 4.5.4. The following subgroups will be based on:

- The four groups resulting from combinations of the two stratification factors:
 - Concomitant MMF treatment (yes/no)
 - o Presence/absence of IPAF as defined by the MDT
- Gender: Male, Female
- Age (years): <65 years, ≥ 65 years
- Percent predicted FVC at Baseline: <65%, ≥65% to < 80%, ≥80%
- Percent predicted DLco at Baseline: <35%, ≥35%
- Body weight: <60 kg, ≥60 kg
- Previous Biopsy (yes/no)

4.5.8 Sensitivity Analyses for missing data

The robustness of the primary method of estimation described above will be explored by a series of sensitivity estimators based on varying assumptions underlying the multiple imputation strategy.

As the primary analysis for this study was performed in March 2019 the number of patients with missing FVC values at week 24 are known. No data was collected after treatment discontinuation.

3 different approaches will be used to evaluate the robustness of the analysis of the secondary endpoint to the missing at random (MAR) assumption.

Due to the low number, deaths and other intercurrent events have not been considered in the multiple imputation analysis.

